14.1 Withdrawal of Participants from the Study

A participant may be withdrawn from study treatment at any time if the participant, the investigator, or the Sponsor feels that it is not in the participant's best interest to continue. The following is a list of possible reasons for study treatment discontinuation:

- Successful weaning from mechanical ventilation
- Participant withdrawal of consent
- Participant is not compliant with study procedures
- Adverse event that in the opinion of the investigator would be in the best interest of the participant to discontinue study treatment
- Protocol violation requiring discontinuation of study treatment
- Lost to follow-up
- Sponsor request for early termination of study
- Positive pregnancy test (females)

If a participant is withdrawn from treatment due to an adverse event, the participant will be followed and treated by the PI until the abnormal parameter or symptom has resolved or stabilized.

All participants who discontinue study treatment should come in for an early discontinuation visit as soon as possible.

All participants are free to withdraw from participation at any time, for any reason, specified or unspecified, and without prejudice. This will not affect the care they receive, now or in the future.

Reasonable attempts will be made by the investigator to provide a reason for participant withdrawals. The reason for the participant's withdrawal from the study will be specified in the participant's source documents.

12.3 Replacement of Participants

While it is estimated that 24 is a suitable sample size for this study, the actual study sample size of 26 allows for a 10% drop out rate. Therefore, up to two participants who withdraw from the study will be replaced.

15 Protocol Violations

A protocol violation occurs when the participant, investigator, or Sponsor fails to adhere to significant protocol requirements affecting the inclusion, exclusion, participant safety and primary endpoint criteria.

Failure to comply with Good Clinical Practice (GCP) guidelines will also result in a protocol violation. The Sponsor will determine if a protocol violation will result in withdrawal of a participant.

When a protocol violation occurs, it will be discussed with the investigator and a Protocol Violation Form detailing the violation will be generated. This form will be signed by a Sponsor representative and the Investigator. A copy of the form will be filed in the site's regulatory binder and in the Sponsor's files.

16 Protocol Amendments

Amendments to the clinical investigation plan must be submitted to the Sponsor for review before submitting to the appropriate IRB for approval.

17 Statistical Methods and Considerations

Only participants who fulfil the protocol in terms of eligibility, interventions and outcome assessment will be included in the statistical analysis. Patient variables will be presented using means and standard deviations for continuous normally distributed variables, medians and interquartile ranges for continuous non-normally distributed variables, and proportions and absolute numbers for categorical variables.

Adverse event rates will be coded by body system and MedDra classification term. Adverse events will be tabulated by treatment group and will include the number of patients for whom the event occurred, the rate of occurrence, and the severity and relationship to study treatment.

Study results will first undergo descriptive level statistical analyses. For continuous variables, Two-way, Student's t-tests will then be carried out using unequal variances where the variables are normally distributed. Tests for normality will be carried out using the Shapiro-Wilk method. Variables that are not normal in distribution that also cannot be log transformed to a normal distribution curve will be analysed using the Mann-Whitney U test or other non-parametric methods to be determined based on actual data distributions.

In the second level of analysis, we will quantify the magnitude to which abdominal NMES exhibits a protective effect. Crude and adjusted linear regression models will be carried out where the outcome variable is continuous and the covariates are normally distributed or categorical. Our prior experience with measures of respiratory function, which will be measured in this study, indicate that select covariates may need to be controlled for or otherwise do not always fit a normal distribution. Therefore, crude and adjusted generalized linear models are anticipated. These regression models will be carried out at the point of successful wean. All multiple regression covariates, linear or generalized, will be assessed for interaction, collinearity and confounding. For all unadjusted and adjusted multinomial models the overall model log likelihood ratio and Hosmer and Lameshow goodness-of-fit will be conducted to ensure models report significance and are not over fitted. Adjusted regression models will undergo sensitivity analysis and bootstrap analyses. Bootstrap analysis is a re-sampling strategy to estimate the population parameter of interest based on the observed, sample data.

The number of tries to successful wean will be quantified using Poisson regression. Crude and adjusted models will be carried out. Kaplan-Meier survival analysis will be carried out to quantify differences in the time to wean in the treatment abdominal NMES modality compared to the control. As the patients will be resident in hospital facilities, we do not anticipate significant methodological concerns with respect to censoring.

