FEV1	Forced Exhaled Volume in 1 second
FVC	Forced Vital Capacity
GCP	Good Clinical Practice
HIPAA	Health Insurance Portability and Accountability Act of 1996
ICH	International Conference on Harmonisation
IEC	Independent Ethics Committee
IRB	Institutional Review Board
MAUDE	Manufacturer and User Facility Device Experience
MEP	Maximum expiratory pressure
MIP	Maximum inspiratory pressure
MV	Mechanical ventilation
NMES	Neuromuscular electrical stimulation
PEF	Peak expiratory flow
PI	Principal Investigator
PTPdi	Pressure-time products of the diaphragm
PTPga	Pressure-time products of the gastric space
SAE	Serious adverse experience
SBT	Spontaneous breathing trial
SCI	Spinal Cord Injury
SPO2	Peripheral capillary oxygen saturation
VAP	Ventilator acquired pneumonia

2 Protocol Synopsis

TITLE	Breath synchronized Abdominal Muscle Stimulation to Facilitate Ventilator Weaning: A Pilot Study
SPONSOR	Liberate Medical, LLC
FUNDING ORGANIZATION	Liberate Medical, LLC
NUMBER OF SITES	1
RATIONALE	
In the U.S. over 500,000 patients have difficulty weaning from mechanical ventilation every year. These patients cost the health care system \$16 billion annually and have an increased risk of medical complications and morbidity.
 
A major factor responsible for weaning failure is the imbalance between decreased respiratory muscle strength and excessive respiratory load. VentFree (Liberate Medical, LLC) is an investigational device that applies electrical stimulation to the abdominal muscles in synchrony with exhalation. This is hypothesized to improve the strength of the respiratory muscles. The long term goal of this project is to determine whether this approach can reduce the number of days taken for patients to wean from mechanical ventilation.

STUDY DESIGN	This is a single center, participant blinded randomized placebo controlled pilot trial.
PRIMARY OBJECTIVE	The primary objective of this study is to determine whether NMES applied to the abdominal wall muscles in synchrony with exhalation can increase the strength of the respiratory muscles in prolonged mechanical ventilation patients
SECONDARY OBJECTIVES	The secondary objectives of the study is to evaluate whether this intervention also affects: (1) the thickness of the abdominal wall muscles and the diaphragm, (2) functional respiratory measurements, and (3) weaning outcome
NUMBER OF PARTICIPANTS	Twenty six: 13 in the treatment arm and 13 in the control arm.

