9.2 Blinding

The difference between active and placebo stimulation can be distinguished visually as active stimulation causes a tetanic muscle contraction whereas placebo stimulation causes a sub-tetanic muscle contraction. Therefore study personnel who apply the treatment to subject will not be blinded to study patients' treatment group assignment.

The following procedures will be used to ensure that patients are blinded to the treatment group that they have been assigned to:

- Study personnel will be instructed not to inform patients as to whether a tetanic or twitch contraction is the active or placebo treatment arm of the study.
- The appearance of the active and placebo stimulation devices will be identical.

In addition, all clinical staff not involved in the study and all study personnel who do not apply stimulation to patients will be blinded to the treatment group assignment of participants. This measure will help ensure that decisions to attempt weaning are unrelated to the study and are only based on clinical care.

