9.4 Number of Study Devices

Four stimulation timing controllers (manufactured by Liberate Medical, LLC) will be used for the study. Two devices will be used for the active stimulation group and two devices will be used for the placebo stimulation group. This will allow one operational device and one back up device per treatment group

Four Empi Continuum stimulators will be used for the study. Two devices will be set to deliver active stimulation and two devices will be set to deliver placebo stimulation. This will allow one operational device and one back up device per treatment group. The Empi Continuum is an FDA cleared stimulator for multiple patient use.

Six sets of electrodes will be provided per participant enrolled in the study to enable a new set of electrodes to be used every week that a patient is enrolled in the study. The PALS Platinum electrodes are FDA cleared electrodes that can be used multiple times with a single patient. 132 sets of electrodes will be used in total.

One variable orifice pneumotachograph will be provided per patient enrolled in the study (26 provided in total). The Braebon variable orifice pneumotachographs are FDA cleared and can be used multiple times with a single patient.

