18.2 Availability and Retention of Investigational Records

The Investigator must make study data accessible to the monitor, other authorized representatives of the Sponsor (or designee), IRB/IEC, and Regulatory Agency (e.g., FDA) inspectors upon request. A file for each participant must be maintained that includes the signed Informed Consent, HIPAA Authorization and copies of all source documentation related to that participant. The Investigator must ensure the reliability and availability of source documents from which the information on the CRF was derived.

All study documents (patient files, signed informed consent forms, copies of CRFs, Study File Notebook, etc.) must be kept secured for a period of two years following the completion of the study. There may be other circumstances for which the Sponsor is required to maintain study records and, therefore, the Sponsor should be contacted prior to removing study records for any reason.

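### Section 15 lets the sponsor decide case by case which protocol violations lead to withdrawal, with no criteria and no requirement that the decision be blind to arm or outcome

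*Combined protocol and SAP*

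**What the plan says.** **Who decides.** Section 15 (Protocol Violations): "The Sponsor will determine if a protocol violation will result in withdrawal of a participant". Section 14.1 lists the matching reason for stopping: "Protocol violation requiring discontinuation of study treatment".

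**What counts.** Under Section 15 a violation arises when the participant, the investigator or the sponsor "fails to adhere to significant protocol requirements affecting the inclusion, exclusion, participant safety and primary endpoint criteria". A failure to follow GCP also counts. The plan does not say which violations lead to withdrawal.

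**Safeguards.** The violation is discussed with the investigator and recorded on a form: "This form will be signed by a Sponsor representative and the Investigator". Section 14.1 has the reason for withdrawal noted in the source documents.

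**The sponsor's position.** The Synopsis says "VentFree (Liberate Medical, LLC) is an investigational device", and Section 9.4 says "Four stimulation timing controllers (manufactured by Liberate Medical, LLC) will be used for the study". The same company is named as sponsor and funder.

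**Blinding.** Besides patients, Section 9.2 says that "all clinical staff not involved in the study and all study personnel who do not apply stimulation to patients will be blinded". It does not mention the sponsor. Section 9.5 limits the meaning of the device colour code to the research team.

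**Data flow.** CRFs are completed as each visit's information becomes available (Section 18.1) and are submitted to the sponsor (Section 18.4). Section 18.2 adds: "The Investigator must make study data accessible to the monitor, other authorized representatives of the Sponsor", on request. Sponsor representatives make the monitoring visits (Section 18.3).

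**After withdrawal.** Section 12.6 and Appendix A plan one early-withdrawal measurement of MIP and MEP, if the patient consents. Section 12.6 has days to wean recorded at that visit only when weaning was the reason for withdrawal. Section 17 restricts the analysis to participants who meet the protocol on eligibility, interventions and outcome assessment.

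**The concern.** Withdrawal after randomisation is harmless to the comparison only if it is unrelated to arm and outcome. Here an interested party makes the decision without written criteria, and nothing stops it from seeing MIP, MEP or the weaning course first. With 12 or 13 patients per arm, two to four selective removals can shift the estimated difference noticeably. Even if every decision is fair, the trial could not show this afterwards.

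The stakes go beyond the pilot's own comparison. The stated primary objective is whether stimulation increases respiratory muscle strength, and Section 17.1 uses the secondary-endpoint data to size the next trial.

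**Working it through.** **1. Path from decision to result.** Three provisions act together.
- Section 15 supplies the discretion.
- Sections 18.1 to 18.4 make participant-level results available to the sponsor, and no masking is described.
- Section 17 turns a withdrawal into an exclusion from the analysis.

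On knowledge of arm the documents are indirect. Section 9.2 is silent on the sponsor. Under Sections 9.3 and 9.4 each device is locked to one arm, and under Section 9.7 device failures are discussed with the sponsor, so discussing a particular device could reveal the arm.

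**2. Are violations plausible?** No rate is given, but some technical violations are likely because the text is inconsistent. The ventilation criterion is worded differently in the Synopsis (at least fourteen days) and in Section 8.2 (more than fourteen). Section 12.3 is headed Day 23 but names day 21 as ideal. Those passages need reconciling in any case.

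**3. The plan's own figure.** Target 24 with 10% dropout: 24/(1 − 0.10) = 26.7, and 24 × 1.10 = 26.4. The stated 26 is reproduced to within rounding and gives 13 per arm. The plan has no figure for violations or their effect.

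**4. Size of the possible bias.** Assumptions: no true effect; normal outcome with SD 1; 13 per arm; Welch test (the unequal-variance test of Section 17) at an assumed two-sided 5%; no replacement of withdrawn participants. A share *v* of participants has a violation by chance. A violator is removed if the reading known at that time looks unfavourable to the device (active below average, placebo above). That reading correlates *r* with the final one.

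Expected spurious difference, in SD:

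2 × (v/2) × r × √(2/π) / (1 − v/2), with √(2/π) = 0.798

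- v = 0.10, r = 1: 2 × 0.05 × 0.798 / 0.95 = 0.084
- v = 0.20, r = 1: 2 × 0.10 × 0.798 / 0.90 = 0.177
- v = 0.30, r = 1: 2 × 0.15 × 0.798 / 0.85 = 0.282

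Multiplying by r gives 0.059, 0.124 and 0.197 for r = 0.7, and 0.042, 0.089 and 0.141 for r = 0.5. Expected removals in total are 26 × v/2 = 1.3, 2.6 and 3.9.

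Simulation (40,000 trials per case), significant results favouring the device, nominal 2.5%:

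| Knowledge at withdrawal | v = 10% | v = 20% | v = 30% |
|---|---|---|---|
| r = 1 (upper bound) | 3.9%, 0.08 SD | 6.1%, 0.18 SD | 9.7%, 0.28 SD |
| r = 0.7 | 3.6%, 0.06 SD | 4.7%, 0.12 SD | 6.3%, 0.19 SD |
| r = 0.5 | 3.1%, 0.04 SD | 4.1%, 0.09 SD | 4.9%, 0.14 SD |

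Repeat runs differ by up to about 0.4 percentage points.

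**5. Under a fixed, blind rule.** With 2, 3 or 4 chance violators per arm, all removed regardless of arm and result, the bias is about 0.00 SD and the two-sided error 4.9%. Analysing all 13 per arm as randomised gives the same.

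**The case against.** **The harm comes from Section 17.** Largely true. Section 15 biases the comparison mainly because Section 17 then leaves the person out, and Section 17 names no one to judge who fulfils the protocol. A fix confined to Section 15 would leave that route open. Section 15 still matters separately: withdrawal ends scheduled assessments, and changing the analysis set afterwards cannot recover those readings.

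**Withdrawn participants still have data.** A reader might infer that a withdrawn participant has no further readings, so that an all-randomised analysis would not help at all. The documents do not support this. Sections 12.6 and 14.1 and Appendix A plan an early-withdrawal visit with MIP and MEP, subject to consent, and an all-randomised analysis could use it. What is lost is the later scheduled readings and later weaning follow-up.

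**The sponsor may be blinded.** A reader might also infer that the sponsor knows the arm. The documents do not say so. The group in Section 9.2 of study personnel who do not apply stimulation could include sponsor staff, and the colour code is kept to the research team. Data access is on request, without stated timing. The text under Section 13.3 (Medical Monitoring) was not available for this check, so a masking provision there cannot be ruled out. What stands is that Section 15 itself sets no such requirement.

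**There are safeguards.** Violations are limited to significant requirements (apart from the GCP clause), the investigator is consulted, both sides sign and the reason is recorded. These make a decision traceable, but they neither fix criteria nor keep results from the decider.

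**The upper bound is unrealistic.** Accepted. Before the Final Visit the decider can know only the baseline, the Intermediate Visit and the weaning course. The rows for r = 0.5 and 0.7 are the more realistic ones, though those correlations are also assumed.

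**Conclusion.** The concern holds as a weakness in the rule for removing participants. The sponsor's decision is discretionary, comes after randomisation and is not required to be blind; through Section 17 it determines who is analysed.

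The size is modest under realistic knowledge: about 3% to 6% false positives in the device's favour instead of 2.5%, with a spurious difference of 0.04 to about 0.2 SD. The ceiling is about 4% to 10% and 0.08 to 0.28 SD. All of this rests on assumed violation rates of 10% to 30%, an assumed 5% two-sided level and selective removal.

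Removing exactly the worst active and the best placebo participant would give 12.3% and 0.28 SD. That should not be read as an expected size, because it needs violations in precisely those two people. Nor do the documents suggest that the sponsor intends to remove participants selectively; they show only that the plan would not prevent or reveal it. The pilot label lowers the stakes but does not remove them, given the stated objective. The change is worth making because it is cheap.

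**What to change.** Replace the sentence in Section 15 with wording to this effect:

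- Withdrawal or exclusion for a violation, on other than safety grounds, is decided against a list fixed before the first participant is randomised. The decision is made by an existing team member or sponsor staff member without access to arm, MIP, MEP or weaning data, and is dated on the Protocol Violation Form.
- A violation alone does not end outcome assessment. The remaining scheduled assessments are carried out unless consent is withdrawn.
- The same pre-specified, blinded decision governs any exclusion under Section 17.

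In Section 17, add an analysis of all randomised participants who have data, including early-withdrawal readings. In Section 9.2, state whether sponsor staff are blinded, and which ones. Safety decisions and the rules on stopping treatment stay as they are.

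Cost: a few sentences of protocol text, one list, one line on an existing form and one extra analysis. The sponsor gives up case-by-case discretion, and a few more assessment visits are completed.

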Each participant will receive either active or placebo electrical muscle stimulation to the abdominal wall during exhalation for sixty minutes per day, five days per week for the shorter of six weeks or until the patient is weaned from mechanical ventilation. Participants will be assigned to active or placebo stimulation in random order (using a random number generator). Evaluations will be performed at baseline, after three weeks of treatment and at the end of treatment. A flow diagram of the study protocol is shown in Figure 3

[figure not shown]

Figure 3 Study Flow Diagram

The maximum duration of participant participation is 45 days. The total duration of the study is expected to be 6 months.

7 Outcome Measures

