11.9 Maximum Expiratory Pressure and Maximum Inspiratory Pressure

Maximum Expiratory Pressure (MEP) and Maximum Inspiratory Pressure (MIP) will be measured at the Baseline Visit, Intermediate Visit, and Final Visit using a cuff inflated cannula as described by Vitacca et al.²¹

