17.1 Sample Size

This study is intended to be a pilot study that will be used to obtain initial data on the feasibility and safety of VentFree to assist in the process of ventilator weaning. The primary outcome of this study is the effect of abdominal NMES on respiratory muscle strength over time. There is currently no data in the literature to support a sample size calculation for this study. Given this constraint, in this pilot study a total of 24 participants was deemed adequate and is consistent with sample size recommendations in the literature.¹ Allowing for a 10% drop out rate, up to 26 participants will be recruited for this study. The data collected on the secondary endpoints will be used to determine the participants needed for a future randomized controlled trial of the device on weaning outcome.

18 Data Collection, Retention and Monitoring

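### The MIP and MEP comparison has no stated baseline term and does not fix final value or change; a baseline-adjusted model should be named in advance

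*Combined protocol and SAP*

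**What the plan says.** Section 7.1 makes MIP and MEP the primary outcome measure without naming a visit or a summary. Section 17.1 words the outcome as follows: "The primary outcome of this study is the effect of abdominal NMES on respiratory muscle strength over time". Section 11.9 states that both pressures "will be measured at the Baseline Visit, Intermediate Visit, and Final Visit using a cuff inflated cannula". Section 12.6 and the Appendix A schedule add a measurement at the Early Withdrawal Visit. Section 6 says: "Evaluations will be performed at baseline, after three weeks of treatment and at the end of treatment".

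Section 17 gives one rule for all continuous variables: "t-tests will then be carried out using unequal variances where the variables are normally distributed". A variable that is not normal, and that a log transform does not make normal, goes to Mann-Whitney or another non-parametric method.

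A second level of analysis follows, in which crude and adjusted "linear regression models will be carried out where the outcome variable is continuous and the covariates are normally distributed or categorical". On the choice of covariates, the text says only that "select covariates may need to be controlled for or otherwise do not always fit a normal distribution". It then adds: "These regression models will be carried out at the point of successful wean".

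Section 17 also confines the analysis to participants who met the protocol on eligibility, treatment and assessments.

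**The concern.** The primary comparison is left open at the point where a small trial is most sensitive to it. A two-group test can be run on the final value or on the change from baseline. Both are valid, but on the same 24 patients they often give different answers. Baseline strength is measured in everyone and is the obvious covariate, yet no stated test uses it and no stated model names it.

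The second-level models do not close the gap. Their covariates are unnamed. They also limit linear regression to normally distributed or categorical covariates, a condition that linear regression does not need; the assumption concerns the residuals. (No harm is claimed from the generalized linear models offered as the alternative.) If the sentence on the point of successful wean applies to MIP and MEP, a patient who never weans has no such point. The comparison would then be made among patients selected on an outcome that the device is meant to affect.

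**Working it through.** **The plan's own figure.** The only sample-size figure is 24 raised to 26 for 10% dropout. 24/0.9 = 26.7 and 24 × 1.1 = 26.4, so 26 agrees to within rounding. There is no power calculation to reproduce.

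**Inputs.** From the documents: 12 per arm (Section 6), 1:1 allocation (Section 9.1). Assumed, because the documents give no figure: true difference 0.8 SD, two-sided 5%, equal SD at both times, baseline-to-follow-up correlation r = 0 to 0.8.

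**Formulas**, in SD units with n per arm and power from the noncentral t:
- Final value: variance 2/n, df 2n − 2.
- Change: variance 2(1 − r)(2/n), df 2n − 2.
- Baseline-adjusted: variance (1 − r²)(2/n)(1 + 1/(2n − 4)), df 2n − 3.

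Example, n = 12 and r = 0.5. Final value: 2/12 = 0.1667, noncentrality 0.8/√0.1667 = 1.96, power 46.6%. Change: 2 × 0.5 × 0.1667 = 0.1667, the same power. Adjusted: 0.75 × 0.1667 × 1.05 = 0.1313, noncentrality 2.21, power 55.8%.

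| r | Final value | Change | Adjusted (ordinary SE) | Adjusted minus better t-test |
|---|---|---|---|---|
| 0 | 46.6% | 26.3% | 44.6% | −2.0 |
| 0.3 | 46.6% | 35.4% | 48.1% | +1.5 |
| 0.5 | 46.6% | 46.6% | 55.8% | +9.2 |
| 0.7 | 46.6% | 67.7% | 72.4% | +4.7 |
| 0.8 | 46.6% | 84.2% | 86.0% | +1.8 |

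The 95% CI half-widths, in SD and in the same order of r, are 0.87/0.83/0.75/0.62/0.52 adjusted, 0.85 throughout for final value, and 1.20/1.00/0.85/0.66/0.54 for change. With 10 per arm (assumed), power is 37/40/47/63/78% adjusted, 40% for final value and 22/30/40/59/76% for change.

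**How often the two t-tests disagree** (simulated unequal-variance tests, 12 per arm). At 0.8 SD: 29.5/30.9/34.1/40.9/47.0% of trials. With no true difference: 6.8/7.6/8.1/8.8/8.9%; at least one of the two is then significant in 8.3/8.7/9.0/9.4/9.4%, against a nominal 5%.

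**Which standard error.** The plan's t-test allows unequal variances, so the adjusted model should too. In simulations with no true difference, r = 0.5, 8 to 10 against 12 patients and a 1.5- to 2-fold larger residual SD in the smaller arm (all assumed), the ordinary model's type I error is 5.9-8.5%. The unequal-variance t-tests stay near 5%. Two heteroscedasticity-consistent standard errors, referred to the t distribution, compare as follows:
- HC2 matches the ordinary model's power with equal arms and variances. Its type I error reaches about 6.6% at 8 against 12 with a 2-fold SD ratio.
- HC3 stays below 5%. With equal arms its power is 39.6/42.7/50.2/67.6/82.7%, about 4-6 points below the ordinary model. Against the better t-test in the table, that is −7.0/−3.9/+3.6/−0.1/−1.5 points.

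**The case against.** The strongest reply is that baseline adjustment is not ruled out. Adjusted models are planned, the text refers to experience with respiratory measures that need covariate control, and the wording about strength over time points towards change. If change is meant and r is 0.7 or 0.8, adjustment gains only about 5 or 2 points. The trial is a pilot that states no alpha and no power target. All of this stands, and it limits the importance. It does not settle which variable, visit or covariate is used.

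Three stronger readings are tempting, and the documents do not support them:
- A reader might infer a type I error of 8-9%. That arises only if the choice is made after seeing both results, and nothing says this will be done. Either test, fixed in advance, holds 5% under the conditions simulated.
- A reader might infer that the primary comparison is confined to weaned patients. The wean sentence belongs to the regression models; the first-level tests carry no such limit. Its application to MIP and MEP is one reading.
- A reader might infer that the unequal-variance t-test is the wrong method. It is valid; the fault is that its variable is not named and collected information goes unused.

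A further objection concerns the remedy. Patients who wean would be measured at a time that treatment may affect, and the rule limiting analysis to protocol-fulfilling participants could remove the early-stop values that the remedy needs. Both are fair, and the fix addresses them.

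**Conclusion.** The concern holds as a gap in specification with a cheap, better alternative. The stated test of the primary outcome uses no baseline value, no section fixes final value or change, and the adjusted models name no covariate. The exclusion of non-weaners is conditional on how one sentence is read.

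The main benefit of the fix is one estimate fixed in advance, which removes a choice on which the two t-tests would differ in about 29-47% of trials at 0.8 SD. Efficiency is secondary: from 2 points below to 9 points above the better t-test with the ordinary or HC2 standard error, and mostly no gain with HC3. These sizes rest on the assumed 0.8 SD difference, 12 per arm and r from 0 to 0.8. Importance is low to moderate.

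**What to change.** In Section 17, for MIP and separately for MEP:

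1. Make the main analysis a linear model of the end-of-treatment value on arm and the baseline value of the same measure. End of treatment is the Final Visit value or, for those who stop early, including through weaning, the Early Withdrawal Visit value. Section 14.1 already asks for this visit: "All participants who discontinue study treatment should come in for an early discontinuation visit as soon as possible". Section 12.6 makes the measurement subject to consent.
2. Include all randomised patients with both values, and state that the protocol-fulfilling rule does not remove early-stop values from this analysis.
3. Choose HC2 or HC3 with a t reference in advance, and report the ordinary model-based interval alongside.
4. For these models, drop the covariate-normality condition and the point-of-wean restriction, and check residuals instead.
5. Report measurement timing and the number missing by arm, and note that weaners are measured at a treatment-dependent time. Give the Intermediate Visit analysis (Day 23 in the schedule) with the same model as a supportive check; patients who stop before that visit may have no value there.
6. Keep the t-test or Mann-Whitney as supportive, and state which variable it uses.

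The cost is wording only, since every measurement is already scheduled. Statistically, it takes one degree of freedom and about 2 points of power if r is near 0. The standard error is a trade-off: HC2 may let type I error rise to about 6.6% in the adverse case simulated, and HC3 gives up about 4-6 points of power.
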